## **Design**

We recruited 30 male and female adults (age 18-65) with OCD and 30 age-, sex-, and education-matched healthy (medically, neurologically and psychiatrically) controls for this project. Each participant came for three sessions. There were 3-8 days interval between sessions:

Session 1 that included initial clinical assessment and obtaining T1 structural image.

Session 2 and 3 that included performing two separate decision-making and symptom provocation-avoidance tasks (see below for more information) by participants with OCD and healthy controls under two conditions: while scanned inside the MRI scanner (no tDCS) or while receiving tDCS neurostimulation outside the scanner (no fMRI imaging). As participants performed each task twice, there might be an order effect on task performance. For minimizing the impact of such a potential order effect on imaging and tDCS results, participants were randomly assigned to undergo scanning in the session 2 and then receive tDCS in the session 3

or in the opposite order (tDCS in session 2 and then imaging in session 3) but in each session only one of imaging or tDCS experiments (for both tasks) could be conducted for each participant.

OCD-relevant and aversive picture rating (explained below) could be done always in the session 3 as the last experiment.

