### **Methods:**

We examined the activity and connectivity patterns of the arbitration regions that have been previously determined to comprise the right and left inferior lateral prefrontal cortex (ilPFC) and right frontopolar cortex (FPC) in individuals with OCD. We acquired functional magnetic resonance imaging (fMRI) data while participants performed a decision-making (DM) task in which goal-directed and habitual action selection strategies compete to govern behavior control. Furthermore, we tested activity and network connectivity of the arbitration regions during the performance of a more clinically relevant symptom provocation-avoidance (SP-A) task. To additionally probe this mechanism, we used the non-invasive brain stimulation method of transcranial Direct Current Stimulation (tDCS). Excitatory and inhibitory currents applied by tDCS over a targeted arbitration region, the left ilPFC, while participants performed the DM and SP-A tasks to further corroborate whether the target arbitrator has causal effects on task performance and habitual/goal-directed action selection balance.

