## **Behavioral data analysis for neurostimulation experiments:**

The effect of anodal (excitatory), cathodal (inhibitory) or sham tDCS stimulation on the prevalence of model-based (MB) and model-free (MF) action selection (number of trials in which MB or MF strategy could be used for action selection) and their ratio could be tested during the decision-making task performance. ANOVA and linear mixed-effects model could be applied, respectively, to compare the effect of different stimulation conditions (anodal, cathodal and sham) on behavioral performance and to compare the effect of two active stimulations (anodal, cathodal) as separate condition factors against sham, while controlling for the time factor between baseline (imaging with no tDCS) and tDCS sessions and treating participants as random effects. For symptom provocation-avoidance task, the effect of anodal, cathodal or sham tDCS stimulation could be evaluated on the timing of avoidance behavior (the duration of time that participants tolerate the OCD-relevant or aversive pictures before pushing the stop button).

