## ***Imaging (fMRI) data analysis:***

In the 1st level (within subject) analysis, we could contrast BOLD signal during decision-making, OCD- and aversive- relevant stimuli presentation compared to a (cross-hair) baseline. The General Linear Model (GLM) method with permutation testing for group-level comparisons could be applied to measure the level of activity ***in the regions of interest*** derived from Lee et al. study for the arbitration (the right and left ilPFC and right PFC), habitual (posterior putamen and supplementary motor area) and goal-directed regions (the vmPFC and caudate) during the decision-making task. For the symptom provocation-avoidance task, the total duration of photo presentation, defined as *avoidance timing*, could be divided into two intervals: 1) starting time of photo presentation until 1-second before pushing the stop button (exposure period), and 2) the 1-second period just before pushing the button. The second interval that

models the avoidance decision period in an approach similar to the Banca et al. study could be focused to test our hypotheses. For all regions mentioned above, activity level could be measured during the avoidance decision period (1 s) by employing GLM with permutation testing for group-level comparisons.

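### The tDCS mixed model treats the imaging session as an unstimulated baseline for everyone, although participants randomised to tDCS first have it after stimulation; carry-over can attenuate the estimate, and neither model states a session-order term

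*Combined protocol and SAP*

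**What the plan says.** Each participant does both tasks twice, once in the scanner without stimulation and once under tDCS. The Design section allocates the order of these two sessions at random. Some participants are scanned first, and the rest do the reverse: "or in the opposite order (tDCS in session 2 and then imaging in session 3"). On spacing it says: "There were 3-8 days interval between sessions". It concedes the practice problem, "As participants performed each task twice, there might be an order effect on task performance", and gives randomised order as the remedy, "For minimizing the impact of such a potential order effect on imaging and tDCS results".

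The Methods section makes clear that the left ilPFC receives current during task performance: "while participants performed the DM and SP-A tasks to further corroborate whether the target arbitrator has causal effects on task performance".

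The section on behavioural analysis of the neurostimulation experiments names an ANOVA across anodal, cathodal and sham. It also names a linear mixed model of the two active conditions against sham, "controlling for the time factor between baseline (imaging with no tDCS) and tDCS sessions and treating participants as random effects". It does not say whether the ANOVA uses tDCS-session data only. Avoidance timing is given no baseline and no model.

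For imaging, the plan says: "The General Linear Model (GLM) method with permutation testing for group-level comparisons could be applied to measure the level of activity". The left ilPFC is among the regions examined. No term for session order or prior stimulation is stated, and no stratification of the order randomisation by diagnosis.

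**The concern.** For a participant scanned first, the imaging session is a true pre-stimulation measurement. For a participant who had tDCS first, it is a second performance of the same tasks, and the first was done under anodal, cathodal or sham stimulation. The analysis section gives both the same label.

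Randomised order and a time term deal with practice that is common to all conditions. They cannot absorb an effect that depends on which stimulation came first. If something learned under active current lasts until the scan, the comparator in the mixed model already contains part of the effect being estimated.

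The same scans feed the OCD-control comparison. With an even order split and three equal conditions (neither is stated), 60 x 1/2 x 2/3 = 20 of the 60 scans follow active stimulation of a region of interest. They would be pooled with unstimulated scans without any term to mark the difference.

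**Working it through.** **Inputs from the documents.** 30 OCD and 30 controls; three stimulation conditions; two session orders; 3-8 days between sessions; d = .77 and .65 from the cited comparable tDCS study, with stated power .97 and .92.

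**Assumptions, not in the documents.** Two-sided alpha .05; 20 participants per condition, each with one condition; half in each order; outcome SD 1; within-person correlation rho = .4 to .8; a share c of the stimulation effect remaining at a later imaging session, c = 0 to .5.

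**The plan's power figures.** A within-person t test with n = 30 gives .983 for d = .77 and .931 for d = .65, within 2 points of the stated values. A between-person comparison of 20 v 20 gives .660 and .517. The stated power therefore appears to rest on a within-person contrast, whose natural comparator here is the imaging session.

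**Mixed model, active v sham.** With a random intercept and no condition effect allowed at imaging, the estimate is the condition difference at the tDCS session minus rho times the difference at the imaging session. The first is d. The second is c*d in the tDCS-first half and 0 in the rest, so c*d/2 on average.

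- Expected estimate = d(1 - rho*c/2)
- Standard error = sqrt(2/20) x sqrt(1 - rho^2); at rho = .6 this is .316 x .8 = .253

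An exact generalised least squares run (3 conditions x 2 orders x 10, d = .77) agrees. The ratio is the same with or without a chronological visit term.

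| rho | estimate/truth, c = .25 | c = .5 | SE, plan's model | SE with carry-over terms |
|---|---|---|---|---|
| .4 | .95 | .90 | .290 | .300 (+3%) |
| .6 | .925 | .85 | .253 | .276 (+9%) |
| .8 | .90 | .80 | .190 | .227 (+19%) |

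At c = 0 the ratio is 1. With carry-over of opposite sign it exceeds 1 by the same amount (1.075 and 1.15 at rho = .6). With prior-anodal and prior-cathodal terms at the imaging session, the bias is 0.

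**tDCS-session data alone.** The imaging session does not enter, so the expected estimate is d at any c. In simulation it stayed at about .77 throughout. The standard error is sqrt(2/20) = .316.

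**Common practice effect.** A shift of .3 SD in all conditions left the active-v-sham estimate at .77 when order was in the model and c = 0.

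**OCD-control fMRI difference.** If the order split is the same in both diagnoses and the order effect is equal, the bias is 0. Otherwise bias = order effect x difference in order split. With unstratified 1:1 allocation in 30 + 30, the split differs by .10 on average, and by .20 or more in about 15% of allocations. For an order effect of .2 to .5 SD, the bias is .02 to .05 SD at a difference of .10, and .04 to .10 SD at .20.

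**Cost of an order term in that model.** The mean squared imbalance is 2 x .25/30 = .0167. The variance inflation is about 1/(1 - .0167) = 1.017, so the standard error rises by just under 1% if there is no order effect, and falls if there is one.

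**The case against.** The strongest reply is that nothing in the documents shows carry-over. Sessions are 3-8 days apart, order was randomised for this very reason, and physiological after-effects may well have gone. That stands. A reader might infer that the tDCS effect is in fact shrunk, but this needs a persisting, same-direction, condition-specific effect, and c is purely an assumption.

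A second reply is that the plan's model is often the more accurate one. At c = .25 its root-mean-square error is below that of the carry-over model at every rho: .292 v .300, .259 v .276 and .205 v .227 for rho = .4, .6 and .8. At c = .5 the two are level or nearly so at rho = .4 and .6 (.300 v .300, .278 v .276), and the carry-over model wins only at rho = .8 (.244 v .227). This also stands, and is why the carry-over model belongs in a sensitivity analysis.

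Third, a reader might infer that the OCD-control imaging result is biased by stimulation history. The documents do not support that, because randomised order makes the default consequence added variance. A shift of .25 SD can be produced by supposing that second exposure moves controls by .5 SD and OCD participants not at all. No section supports that scenario, and it describes practice differing by diagnosis, not carry-over of stimulation.

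What the replies do not remove is the label itself and the absence of session order from both stated models.

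**Conclusion.** The point holds in limited form. The imaging session is not an unstimulated baseline for participants who had tDCS first, and a time term cannot remove condition-specific carry-over. The mixed-model active-versus-sham estimate can be attenuated by rho*c/2: 5-20% over c = .25 to .5 and rho = .4 to .8, nothing at c = 0, and inflated if the sign is reversed. At rho = .6 the bias is .058/.253 = .23 of a standard error at c = .25 and .46 at c = .5, within sampling noise for a single study. These figures assume equal conditions and an even order split.

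It would go too far to say that every tDCS comparison is affected. An anodal-cathodal-sham comparison on tDCS-session data is not. Nor do the documents show that the stated power fails. A simple difference from the imaging session would shrink by c/2, but the plan specifies a mixed model.

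For the fMRI comparison the consequence is mainly variance. Bias needs order imbalance between diagnoses, or an order or stimulation effect that differs by diagnosis. Neither is excluded by the text and neither is shown.

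**What to change.** **Behavioural tDCS analysis.**
- Stop describing the imaging session as baseline for tDCS-first participants.
- Include randomised session order (visit) in the mixed model.
- State that the ANOVA of anodal, cathodal and sham uses tDCS-session data.
- As a sensitivity analysis, add prior-anodal and prior-cathodal terms at the imaging session for tDCS-first participants, and report the active-versus-sham estimates with and without them.

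**Imaging analysis.**
- Add session order (scan first or tDCS first) to the group model and permute within those two strata.
- Report the OCD-control difference in session-2 scans, which are all unstimulated, as a description only. It rests on about 15 per group, so its standard error is about sqrt(2/15) = .37 SD, against sqrt(2/30) = .26 SD for the full sample.

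Keep the full sample and the plan's mixed model as the main analysis. Restricting baseline to scan-first participants would discard it for about half the sample. Permuting within four stimulation-history strata would leave about 5 per diagnosis in three of them. Neither is advised.

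**Cost.** Recruitment is reported in the past tense, so the change is to analysis wording plus a few model runs. The carry-over model raises the standard error by about 3-19% (rho .4 to .8). The fMRI order term costs about 1% if there is no order effect.

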## ***Imaging (fMRI) data analysis:***

In the 1st level (within subject) analysis, we could contrast BOLD signal during decision-making, OCD- and aversive- relevant stimuli presentation compared to a (cross-hair) baseline. The General Linear Model (GLM) method with permutation testing for group-level comparisons could be applied to measure the level of activity ***in the regions of interest*** derived from Lee et al. study for the arbitration (the right and left ilPFC and right PFC), habitual (posterior putamen and supplementary motor area) and goal-directed regions (the vmPFC and caudate) during the decision-making task. For the symptom provocation-avoidance task, the total duration of photo presentation, defined as *avoidance timing*, could be divided into two intervals: 1) starting time of photo presentation until 1-second before pushing the stop button (exposure period), and 2) the 1-second period just before pushing the button. The second interval that

models the avoidance decision period in an approach similar to the Banca et al. study could be focused to test our hypotheses. For all regions mentioned above, activity level could be measured during the avoidance decision period (1 s) by employing GLM with permutation testing for group-level comparisons.
